5.4.2. Withdrawal From the Study

Subjects may withdraw consent for the study at any time or subjects may be lost to follow-up. It is important to obtain follow-up information, according to standard medical practice, on any subject withdrawn prematurely from the study. Every effort must be made to undertake at least standard assessments that are critical for clinical activity or safety evaluation, such as disease progression (if the subject did not withdraw because of disease progression), subsequent anticancer treatment, survival information, and safety data.

If a subject withdraws consent from the study, the sponsor may retain and continue to use any information and data collected or generated up to the time of withdrawal of consent.

Additionally, if a subject withdraws consent, they may request destruction of any samples taken and not tested yet, and the investigator must document this in the site study records and inform the sponsor within 24 hours.

5.4.3. Replacement of Subjects

Subjects will be replaced in this study as needed to achieve the planned number of evaluable subjects in each part of the protocol. See Section 11.1 for the definition of evaluable subjects.

5.4.4. End of Study

The study will be considered complete (that is, scientific evaluation will be complete [study completion]) following evaluation of safety and efficacy as determined by the Sponsor. Investigators will continue to follow the Schedule of Activities (Table 13) for all patients until notified by the Sponsor that study completion has occurred.

End of the study is the date of the last visit or last scheduled procedure for the last patient.

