Note: Other gene aberrations that in the investigator's opinion may confer sensitivity to ASTX029 may be included in Cohort F after obtaining approval from the Sponsor's medical monitor.

For each potential subject, there is an up to 21-day screening and eligibility assessment period before enrollment; the first dose of study treatment will be administered on Cycle 1 Day 1 (C1D1). Subjects will continue to receive their assigned treatments throughout the study until the occurrence of disease progression, death, or unacceptable treatment-related toxicity; they elect to discontinue study treatment or withdraw consent to continue study participation; or until the study is closed by the sponsor.

Study visits will take place weekly during Cycles 1 and 2 and less frequently thereafter (see Table 11 and Table 12 for the complete schedules of events for the Regimen 1 and Regimen 2, respectively). Serial blood samples will be collected for PK and biomarker analyses at specified time points. If a formalin-fixed paraffin-embedded (FFPE) archived tumor biopsy is available, it will be obtained for use in this study during screening. In addition, in Phase 1 Part A and Phase 2, fresh tumor biopsies are optional during screening and posttreatment during Cycle 2. In

Phase 1 Part B, fresh tumor biopsies are mandatory during screening and posttreatment during Cycle 2.

Upon permanent discontinuation of study treatment, there is a Treatment Termination (Tx Term) visit and a 30-day (± 5 days or within 3 days before starting new treatment) Safety Follow-up visit. Subjects who remain on study after the 30-day Safety Follow-up visit will be contacted periodically by telephone for collection of long-term health status information.

Tolerability and safety of study treatment will be evaluated throughout the study by collection of clinical and laboratory data. Antitumor response will be assessed according to standard Response Evaluation Criteria in Solid Tumors (RECIST) v1.1 using computed tomography (CT) or magnetic resonance imaging (MRI) scans. Subjects whose disease is not measurable using RECIST v1.1 will be evaluated using another appropriate method.

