5.4.5. Study Extension

Following Study Completion (see above Section 5.4.4), all patients who are on study treatment and deriving clinical benefit with no undue risk may continue to receive study treatment in a study extension phase or a rollover study until any of the study treatment discontinuation criteria (Section 5.4.1) are met.

During study extension, assessments are to be conducted according to the Schedule of Activities in Table 13. Data collection will be limited and will include (at a minimum):

- Study drug administration
- Study drug accountability
- AEs
- SAEs
- Any cases of pregnancy or overdose

Investigators will perform any other standard procedures and tests needed to treat and evaluate patients; however, the choice and timing of the tests will be at the investigator's discretion. The Sponsor will not routinely collect the results of these assessments.

If an SAE occurs, the Sponsor may request additional information (eg, local laboratory results, concomitant medications, hospitalizations) to evaluate the reported SAE.

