9.4.9. Schedules of Events

Table 11 presents the complete schedule of events for Regimen 1 Continuous Dosing, andTable 12 presents that for Regimen 2 Intermittent Dosing with details following in text. Table 13presents the Schedule of Events for the Study Extension phase.

Clinical and diagnostic laboratory evaluations are detailed before study entry, throughout the study, and at the follow-up evaluation. The purpose of obtaining these detailed measurements is to ensure adequate assessments of preliminary clinical activity, safety, and tolerability. Repeat clinical evaluations and laboratory studies more frequently if clinically indicated.

Note any deviation from protocol procedures. Investigators are responsible for implementing appropriate measures to prevent the recurrence of violations and deviations and to report to their IRB/IEC according to policy.

Table 11: Schedule of Events Regimen 1 – Continuous (Days 1 Through 21) Dosing

Cycle (21 Days) ^a]	1			2	2		≥3 ª	Tx Term ^b	30-day Safety FU ^c	Long- term FU
Cycle Day ^d		1 ^e	2	8	15	1	2	8	15	1			
Study treatment dispensation		x		x	Х	x		x	x	X			
Dosing compliance information				x	х	x		x	x	X	х		
Procedures	Screening ^f												
Informed consent	Х												
Medical history	Х												
Investigator's confirmation of eligibility	Х	x											
PE/symptom-directed PE ^g	Х	x		x	х	x		x	x	x	x	х	
Height	Х												
Weight	Х	x				x				x			
Vital signs ^h	Х	x	x	x	х	x	x	x	x	x	x	х	
ECOG performance status	Х	x		x	х	x		x	x	x	x	х	
12-lead ECG ⁱ	Х	x	x	x	х	x				x	x		
ECHO or MUGA scan	Х	Repe	Repeat every 2 cycles for the first 4 cycles and then every 4 cycles thereafter $(\pm 7 \text{ days})$					x					
Ophthalmic examination ^j	Х												
Concomitant medications/AEsk	Х	x	x	x	х	x	x	x	x	x	x	х	
Randomization (if applicable), enrollment	Х												
Laboratory Assessments													
Hematology ^{1,m}	Х	x		x	X	x		x	x	x	X		
Coagulation ^{m,n}	Х	x				x				х	х		

Cycle (21 Days) ^a			-	1				2		≥3 ª	Tx Term ^b	30-day Safety FU ^c	Long- term FU
Cycle Day ^d		1 ^e	2	8	15	1	2	8	15	1			
Chemistry ^{m,o}	Х	x		x	x	x		х	х	х	х		
Urinalysis ^{m,p}	х	x				x				X	Х		
Serum or urine pregnancy test ^{m,q}	х	x				x				X	X		
Pharmacokinetics ^r		x	x			x	xs			x ^t			
Blood sample for ctDNA ^u	х	x				x				х	X		
Blood (PBMC) sample for germline DNA	х												
Obtain archival tumor tissue ^v	х												
Collect pretreatment biopsyv	х												
Collect on-treatment biopsyv								x					
Disease Assessments													

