Response assessment ^w	х	At th	At the end of every 2 cycles (±7 days) for the first 4 cycles and then every 4 cycles (±1 cycle) thereafter										
Health status follow-up ^x					-								Every 3 months

AE=adverse event; CxDx=Cycle x Day x; CBC=complete blood count; ctDNA=circulating tumor DNA; CT=computed tomography; ECG=electrocardiogram; ECOG=Eastern Cooperative Oncology Group; eCRF=electronic case report form; FFPE=formalin-fixed paraffin embedded; FU=follow-up; INR=international normalized ratio; MRI=magnetic resonance imaging; MUGA=multiple-gated acquisition; PBMC=peripheral blood mononuclear cell; PE=physical examination; PK=pharmacokinetic; PTT= partial thromboplastin time; Tx Term=Treatment Termination.

^a After Cycle 6, the specific visit schedule and assessments are at the investigator's discretion; at a minimum, information should be collected regarding concomitant medications, AEs, dosing compliance, and, at least once a month, pregnancy tests. Continue to collect efficacy and response assessments, in the manner described in the protocol, until disease progression (for response assessment) or death (for survival assessment), or the subject withdraws consent.

^b Perform Tx Term visit procedures when a subject permanently discontinues study treatment, regardless of whether or not the subject plans to continue participating in the study (unless consent to continue study participation is withdrawn by the subject). The visit is to occur within 7 days after the last study treatment or within 3 days before starting new anticancer treatment and before the 30-day Safety Follow-up visit. If a subject discontinues study treatment at a scheduled visit, the assessments at that visit can be used to fulfill the Tx Term visit requirements.

^c The 30-day Safety Follow-up visit must occur 30 (+5) days after the last dose of ASTX029 or within 3 days before starting new cancer treatment.

^d In Phase 1 starting with C2D8, study visits have a visit window of ± 1 day. In Phase 2, all study visits for Cycles ≥ 2 have a visit window of ± 2 days.

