- Serum chemistry must include the analytes listed in Table 10. The C1D1 chemistry evaluations do not need to be repeated if screening tests are within 4 days prior to first dose of ASTX029. On C1D1, all chemistry evaluations must meet study entry criteria before dosing.
- ^p Urinalysis includes dipstick test (if available) and microscopic examination (if indicated) (Table 10). The C1D1 urinalysis evaluations do not need to be repeated if screening tests are within 4 days of first dose of ASTX029.
- ^q Pregnancy test: to be performed at screening, within 24 hours before the start of Cycles 1 through 6, at least monthly during treatment thereafter, and at the Tx Term visit (only for women of child-bearing potential).

- ^r See Table 5 and Table 7, respectively (Section 9.2.1), for the complete PK blood draw schedule for Phase 1 and Phase 2.
- ^s Collect PK blood samples in Phase 2 only; see Table 7.
- ^t See Table 8 for the ctDNA sample collection schedule. On dosing days, predose samples are to be collected within 60 minutes prior to administration of study treatment.
- ^u If archived tumor tissue (FFPE) is available, it will be requested for use in this study during screening. In addition, collection of fresh tumor biopsies is encouraged (optional) in Phase 1 Part A and Phase 2 and mandatory in Phase 1 Part B of the study during screening and on C2D8 (±1 day), 4 hours (±1 hour) postdose. See Table 9 for the biopsy collection schedule.
- ^v CT or MRI scan (or other appropriate disease evaluation method, including tumor marker measurement, as applicable) will be performed at screening, at the end of every 2 cycles (±7 days) for the first 4 cycles, and then every 4 cycles (±1 cycle) thereafter until clinical and/or radiographic disease progression, or death, or the subject withdraws consent, whichever occurs first (Section 9.1, Section 9.4.8. If the last assessment was >12 weeks prior to study treatment withdrawal and disease progression had not been documented, a disease assessment should be obtained at the Treatment Termination visit.
- ^w Beginning 3 months after discontinuation of treatment, subjects will be contacted by telephone for collection of health status information every 3 months until death, the subject withdraws consent, or end of study, whichever occurs first (Section 9.4.15).

Table 13 Schedule of Events – Study Extension Phase

	Treatment Period (1 cycle = 21 days)	Safety Follow-Up	Notes

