	At Least Every 3 Cycles	30 (+5 days) After Last Dose	
Physical examination	X	Х	Only symptom-directed examinations required
Vital signs	Х	Х	Assess all vital signs after the subject has rested in a sitting or semirecumbent position for at least 3 minutes.
Weight	X	Х	
Ophthalmological examination	(X)	(X)	Performed only as symptomatically warranted. Section 9.4.6
ECOG performance status	X	Х	See Appendix 1
12-Lead electrocardiogram	Х	Х	Performed in triplicate, with each recording separated by at least 30 seconds. See Section 9.4.4.
Hematology	Х	Х	Must include CBC with either manual or automated differential and platelet counts. See Table 10
Coagulation	X	Х	Includes PTT and prothrombin time (or INR). See Table 10
Chemistry	X	Х	See Table 10
Pregnancy test	Х	Х	If applicable. Additional testing (urine or serum) as required per local practice.
Concomitant medications/ AEs	X	Х	Collect through 30 days after administration of the last dose of study treatment or until the subject starts of new cancer treatment, whichever occurs first. See Section 7.6 and Section 9.3
Response assessment (CT/MRI)	X		Tumor assessments may be performed as necessary to determine continued benefit from treatment, every 4 cycles $(\pm 1 \text{ cycle})$, or as clinically indicated, until radiologic PD or initiation of new anticancer therapy (whichever occurs first). See Section 9.4.8

AE=adverse event; ECOG=Eastern Cooperative Oncology Group

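### Protocol 5.4.4 cites the extension-phase schedule (Table 13) for the period before study completion, so sites hold conflicting instructions on scans, ECHO/MUGA and survival contact

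*Protocol*

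**What the plan says.** Section 5.4.4 (End of Study) gives investigators a direct instruction: "Investigators will continue to follow the Schedule of Activities (Table 13) for all patients until notified by the Sponsor that study completion has occurred".

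Section 5.4.5 (Study Extension) starts the extension only after that point: "Following Study Completion (see above Section 5.4.4), all patients who are on study treatment and deriving clinical benefit with no undue risk may continue" on treatment. It then assigns the same table to that later period: "During study extension, assessments are to be conducted according to the Schedule of Activities in Table 13".

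The table is titled "Schedule of Events – Study Extension Phase", and Section 9.4.9 describes it in the same way. For the main study, Section 4.1.2 refers the reader to "Table 11 and Table 12 for the complete schedules of events" for Regimens 1 and 2.

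The two kinds of schedule differ on disease assessment. Table 11 requires it "At the end of every 2 cycles (±7 days) for the first 4 cycles and then every 4 cycles (±1 cycle) thereafter". Table 13 says "Tumor assessments may be performed as necessary to determine continued benefit from treatment", giving every 4 cycles (±1 cycle) or clinical indication as the timing.

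**The concern.** One table is assigned to both sides of the completion date, although it was written for one side only. Sections 5.4.4 and 5.4.5 and Table 13 are all listed in the summary of changes as additions in the current amendment, so this is live text addressed to investigators.

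The affected data feed planned analyses. SAP 5.3 and 7.5.1 base ORR on subjects with a baseline and at least one follow-up assessment, plus those who died or stopped early because of clinical progression or toxicity. SAP 7.5.3 censors PFS at the last disease assessment and OS at the last date known alive, and it plans OS rates at 3, 6, 9 and 12 months and beyond. If scans become optional and survival contacts are not scheduled, assessment and censoring dates move. ECHO/MUGA is a safety measure, and Appendix 8 ties LVEF monitoring to Tables 11 and 12, not to Table 13.

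**Working it through.** The plan gives no figure to reproduce here, and sample size, power and alpha do not enter. The check compares the schedules and counts scans.

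**Tables 11 and 13 compared**

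| Item | Table 11 (Table 12 is the same on these items) | Table 13 |
|---|---|---|
| CT/MRI | End of Cycles 2 and 4, then every 4 cycles (±1) | Optional wording; every 4 cycles (±1) or as indicated |
| Scans end at | Clinical and/or radiographic progression, death or withdrawal of consent | Radiologic progression or new anticancer therapy |
| ECHO/MUGA | Every 2 cycles for 4 cycles, then every 4, and at Treatment Termination | No row |
| Treatment Termination visit | Yes | None |
| PK, ctDNA | Yes | No row |
| Survival/health-status contact | Every 3 months | None; ends at the 30-day safety visit |

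**Scan timing.** Cycles last 21 days, so week = cycle × 21/7 = cycle × 3.

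- Table 11 scans fall at the end of Cycles 2, 4, 8, 12, 16, 20 and 24, which is weeks 6, 12, 24, 36, 48, 60 and 72.
- Table 13 scans, if done and counted from the start of treatment, fall at the end of Cycles 4, 8, 12, 16, 20 and 24, which is weeks 12, 24, 36, 48, 60 and 72.
- The first-scan window is 6 ± 1 = weeks 5 to 7 under Table 11. Under Table 13 it is (4 − 1) × 3 to (4 + 1) × 3 = weeks 9 to 15.

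| Through cycle | Table 11 | Table 13, at most |
|---|---|---|
| 4 | 2 | 1 |
| 8 | 3 | 2 |
| 12 | 4 | 3 |
| 24 | 7 | 6 |

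The difference is always one scan, the one at the end of Cycle 2. From Cycle 4 the nominal interval is the same. Because Table 13 words scans as optional, its lower bound is 0 in every row. ECHO/MUGA within the first 4 cycles goes from 2 after screening to 0.

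**What the Cycle 2 scan carries.** Appendix 3 requires no confirmation of response, so a partial response seen at week 6 and gone by week 12 counts under Table 11 but would not be seen under Table 13. A subject who leaves between the two dates for a reason other than death, clinical progression or toxicity, without a scan, would drop out of the ORR denominator in SAP 5.3.

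**What other sections still require.** Section 9.1 requires scans on the Table 11 pattern, and Section 9.4.12 continues response and survival collection after Cycle 6. Section 9.4.5 requires ECHO/MUGA. Sections 5.4.1 and 9.4.15 require contact every 3 months. None of them says whether it or 5.4.4 prevails.

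**The case against.** The strongest reply is that this is a wrong table number and that no site would act on it. Section 5.4.4 speaks of continuing with a schedule, which presupposes the one already in use. Table 13 has no consent, screening, Cycle 1 or dispensing entries, so a new subject could not be run on it. Several other sections give the main-study requirements consistently. This largely stands as an account of how the text arose, and it makes literal compliance in early cycles unlikely. It does not remove the conflict for subjects in later treatment or survival follow-up, for whom Table 13 could be followed. Section 5.4.4 says all patients, and on Table 13 a subject past the 30-day visit has nothing scheduled.

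A second reply is that few subjects may have been exposed in early cycles. SAP 6.0 puts study start in Q2 2018. Adding the 55 months of recruitment in Protocol 12 gives about November 2022 to January 2023. The Amendment 5.0 page header is dated 23 May 2024, some 16 to 18 months later, so if recruitment ran to plan the Cycle 2 scan was no longer at issue. However, SAP 1.0 dates Amendment 5.0 to 14 April 2022, which falls before that point, and actual enrollment is not given. The exposure is unknown in either direction.

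A reader might also infer that the endpoint scans, survival follow-up and ECHO would simply be lost, with both the week 6 and week 12 scans gone. The documents do not support that. Table 13 keeps a CT/MRI row whose first nominal date is week 12, and the sections listed above still require all three assessments.

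**Conclusion.** The contradiction is certain and can be read directly from the text: 5.4.4 conflicts with 5.4.5, 9.4.9, the title of Table 13 and 4.1.2. The consequence is conditional. If a site follows 5.4.4 before completion, the nominal schedule loses one scan (end of Cycle 2), the first reading moves from about week 6 to about week 12, and later scans become optional. ECHO/MUGA, the Treatment Termination visit, PK, ctDNA and 3-monthly survival contact are no longer scheduled. If it follows the other sections, nothing is lost.

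The plan's fault is therefore conflicting instructions under which data for ORR, PFS and OS, and LVEF monitoring, could be missed. This rests on 21-day cycles and on counting Table 13's interval from the start of treatment. For a subject already past Cycle 4 the nominal scan interval does not change, and what remains is the optional wording and the items that Table 13 leaves out. The number of subjects affected cannot be derived from the documents.

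**What to change.** Reconcile 5.4.4 with 5.4.5, 9.4.9, 4.1.2 and Sections 5.4.1, 9.1, 9.4.5, 9.4.12 and 9.4.15, so that one schedule is named for the period before study completion and Table 13 is cited only for the extension phase its title gives. For the endpoints this adds no requirement, because the scans and survival contacts are already written into those sections. The ECHO/MUGA passages need the same reconciliation, and this review takes no position on their frequency.

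The cost is a corrected cross-reference. Section 14.4 allows an administrative letter for obvious errors and inconsistencies, so a full amendment should not be needed. It would also help to ask sites whether any subject was moved to Table 13 before completion, so that missing scans or contacts can be identified before the analysis.

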5.4.5. Study Extension

Following Study Completion (see above Section 5.4.4), all patients who are on study treatment and deriving clinical benefit with no undue risk may continue to receive study treatment in a study extension phase or a rollover study until any of the study treatment discontinuation criteria (Section 5.4.1) are met.

During study extension, assessments are to be conducted according to the Schedule of Activities in Table 13. Data collection will be limited and will include (at a minimum):

- Study drug administration
- Study drug accountability
- AEs
- SAEs
- Any cases of pregnancy or overdose

Investigators will perform any other standard procedures and tests needed to treat and evaluate patients; however, the choice and timing of the tests will be at the investigator's discretion. The Sponsor will not routinely collect the results of these assessments.

If an SAE occurs, the Sponsor may request additional information (eg, local laboratory results, concomitant medications, hospitalizations) to evaluate the reported SAE.

6. ENROLLMENT AND RANDOMIZATION PROCEDURES

Subjects will be screened at each study center for assessment of eligibility for the study. The investigator or designated staff will be responsible for allocating and recording subject identification numbers. Each subject who signs the informed consent form (ICF) will be assigned a unique identification (ID) number that reflects the study center number assigned to the investigator and the subject at that site. The same subject ID number will be used to identify the subject from screening throughout the study and will be entered on all study documents.

A given subject ID number will not be assigned to more than 1 subject. If a subject is not eligible to receive treatment or if the subject discontinues from the study, the subject number will not be reassigned to another subject. A centralized allocation procedure will be used.

See Section 7.3 for the dose-escalation guidelines.

6.1. Randomization

This is an open label study. All enrolled subjects will receive ASTX029. In Phase 1 Part A (dose escalation), initially, only a single dosing regimen (Regimen 1) will be evaluated. Following the occurrence of event(s) meeting prespecified criteria (Section 7.1.4), a second dosing regimen (Regimen 2) may be activated. If the second dosing regimen becomes active, subjects will be assigned following a simple randomization procedure (eg, computerized random numbers) to Regimen 1 (continuous dosing) or Regimen 2 (intermittent dosing).

When only a single regimen is active (eg, the cohort for 1 regimen has completed enrollment, or is on hold), randomization will be suspended, and all subjects will be allocated to the active regimen.

In Phase 1 Part B, if more than 1 dose/regimen is selected, subjects will be randomized in a 1:1 ratio.

When a qualified subject is identified (ie, meets all eligibility criteria), site staff will confirm the subject's eligibility in the Interactive Response Technology (IRT) system. The IRT system will automatically enroll/randomize the subject to the appropriate treatment regimen/cohort and allocate study drug. Details of randomization/enrollment are described in the IRT User Guide.

